### ● Purpose of the study

- To gather baseline data on the prevalence and impact of musculoskeletal symptoms among otolaryngologists in George Washington University Hospital network.
- To examine the influence of otolaryngology stretching micro-breaks (OSMB) on their physical performance, mental focus, and self-reported pain and discomfort among otolaryngologists in George Washington University Hospital network.

### ● Enrollment Criteria

- Age: 18-80
- Attending physicians, residents, and fellows affiliated with The George Washington University and Children's National Medical Center Division of Otolaryngology-Head & Neck Surgery.

### ● Sample size

- N= 26
  - 9 attending physicians and 8 residents at GWU
  - 9 attending physicians at Children's National Medical Center

### ● Recruitment Methods

- An E-mail will be sent out to attending physicians and residents affiliated at GWU and Children's National inviting them to participate in the study.

- **Research Locations**

- George Washington University Hospital
- Children's National Medical Center

[figure not shown]
- **Methods**

- **Intervention**

- **Otolaryngology stretching micro-breaks (OSMB)**= standardized microbreak stretch that is designed to perform intraoperatively within the sterile field at medically convenient 20-40 min intervals throughout each procedure.

- **Assessment tools (see the table of content to view survey)**

[figure not shown]
- Preliminary questionnaire- given at the beginning of the study
    - Assess demographic information, ergonomic questions, and musculoskeletal symptom questions
  - Pre-surgery questionnaire (baseline)- given prior to each surgery to establish a baseline
    - Body part discomfort (validated survey with 0-5 score on the neck, shoulder R/L, hand R/L, lower/upper back, knee R/L, foot R/L)

- Post-surgery questionnaire for CONTROL day- given after each surgery
  - Surg-TLX and GOAL questionnaire- assess the degree of difficulty of the surgery
  - Body part discomfort sore
- Post-surgery questionnaire for INTERVENTION day- - given after each surgery
  - Surg-TLX and GOAL questionnaire- assess the degree of difficulty of the surgery
  - Body part discomfort sore
  - Questions on OSMB
- Exit questionnaire after the study is completed
  - 2 questions asking whether the participant would incorporate OSMB in their routine OR cases, and would recommend OSMB to colleagues.

- **Study design**

- Crossover study design
- Control: 3 Non-OSMB surgical days
- Intervention: 3 OSMB surgical days
- In order to reduce confounding variables, study will focus on open neck cases. (e.g. thyroidectomy, parathyroidectomy, neck dissection, etc)
- We will adjust for surgical duration, and use Surg-TLX, and GOAL questionnaires to show no statistically significant difference between control and intervention surgical cases.
- Outcome measures
  - Primary outcome= difference between self-reported body part discomfort score from before/after surgery
    - Control the surgical environment and difficulty using Surg-TLX and GOAL questionnaires. The score should be statistically insignificant among various surgeries.
  - Secondary outcome= impact of OSMB on physical performance, discomfort/pain, fatigue, and mental focus
  - Tertiary outcome= distraction and workflow interruption of OSMB

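### Symptom prevalence is an aim of its own, but the only described way to the questionnaire is joining the crossover, and eligible fellows appear in neither the invitation nor the N of 26

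*Protocol*

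**What the plan says.** Five places in the protocol bear on who is counted for prevalence.

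- **Purpose of the study.** The first aim is "To gather baseline data on the prevalence and impact of musculoskeletal symptoms among otolaryngologists in George Washington University Hospital network". The effect of the stretching breaks is a second, separate aim. The Statistics section plans descriptive statistics for the first.
- **Enrollment Criteria.** Eligible are "Attending physicians, residents, and fellows affiliated with The George Washington University and Children's National Medical Center". The demographic part of the Preliminary Questionnaire offers Fellow as a surgical title.
- **Sample size.** N is 26, made up of "9 attending physicians and 8 residents at GWU" and "9 attending physicians at Children's National Medical Center".
- **Recruitment Methods.** One e-mail goes to "attending physicians and residents affiliated at GWU" and at Children's National, asking them to take part in the study. Fellows are not named.
- **Assessment tools and Study design (under Methods).** The prevalence items are in the "Preliminary questionnaire- given at the beginning of the study". The study is a crossover of 3 control and 3 intervention surgical days, centred on open neck operations. No survey-only route is described.

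**The concern.** The group the first aim describes and the group the protocol arranges to survey are not the same.

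**Tie to the crossover.** A surgeon who would answer one questionnaire, but who does not want six study days or does few open neck operations, has no stated way to be counted. The questionnaire itself is written for the wider specialty: it asks about microscope, robot and endoscopic instruments. It also asks whether symptoms have made the respondent give up this kind of operation. People who would answer yes may be among those least able to supply the crossover days.

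**Fellows.** They are eligible and the form can record them, but the invitation and the headcount leave them out. The sections cannot all be right.

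At stake is how well the reported prevalence and impact represent the network. In a group of about 26, a few missing people move a percentage noticeably, and no later analysis can recover people who were never surveyed.

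**Working it through.** **1. The plan's own figure.** 9 + 8 + 9 = 26. This reproduces the stated N exactly, so fellows hold 0 of the 26 places. The protocol gives no precision target for prevalence, so there is no sample-size formula to check.

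**2. Inputs the protocol does not give (assumed).** Number of fellows F: 0 to 4. Share of the 26 who join: 60% to 100%, that is r = 26, 21 or 16 people. It is also assumed that 26 is the full roster of attendings and residents; the protocol does not say whether it is a roster or a target.

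**3. Worst-case bounds.** The eligible roster is R = 26 + F. If x of the r people surveyed report symptoms, prevalence in the roster lies between x/R (everyone unsurveyed symptom-free) and (x + R − r)/R (everyone unsurveyed symptomatic). The width is (R − r)/R, whatever x is.

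| Fellows F | r = 26 | r = 21 | r = 16 |
|---|---|---|---|
| 0 | 0/26 = 0 | 5/26 = 19.2% | 10/26 = 38.5% |
| 1 | 1/27 = 3.7% | 6/27 = 22.2% | 11/27 = 40.7% |
| 2 | 2/28 = 7.1% | 7/28 = 25.0% | 12/28 = 42.9% |
| 4 | 4/30 = 13.3% | 9/30 = 30.0% | 14/30 = 46.7% |

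These are outer limits, not expected errors. They need no assumption about why people stay out.

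**4. Direction.** Let p be true prevalence, and a and b the uptake of symptomatic and symptom-free staff. Expected observed prevalence is pa / [pa + (1 − p)b]. With p = 60% (assumed):

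- a = 80%, b = 40%: 0.48/(0.48 + 0.16) = 75%
- a = 80%, b = 60%: 0.48/(0.48 + 0.24) = 67%
- a = b: 60%
- a = 60%, b = 80%: 0.36/(0.36 + 0.32) = 53%
- a = 40%, b = 80%: 0.24/(0.24 + 0.32) = 43%

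The first two suppose that pain makes people keener to join. The last two suppose that symptoms keep people away, for instance because they no longer do these operations. The protocol supports neither over the other.

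**The case against.** The case against is considerable.

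- The aim speaks of otolaryngologists in the network and does not say all of them. Prevalence is not a primary, secondary or tertiary outcome, and its analysis is descriptive only.
- The uneven headcounts by role and site look as much like a full roster as a target. If 26 is the roster and everyone joins, there is no selection among attendings and residents.
- The questionnaire comes before any surgical day, so someone who completes it and then drops out still contributes. The e-mail and consent texts are not available, so what invitees are told cannot be checked.
- The uptake figures are assumed. With 26 on the roster, the 80%/60% case gives about 19 joiners (26 × 0.72 = 18.7), and 67% instead of 60% is about one person.
- There may be no fellows in post.
- Response-rate reporting can be left to the statistical analysis plan.

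All of this limits the size of the point, and a reader should not go beyond it. One might infer that prevalence will be overstated, because surgeons in pain have more reason to try the breaks. Nothing in the protocol links symptoms to uptake, and the item on giving up operations points to a possible pull the other way. One might also infer that fellows are excluded. They are not: the criteria admit them and the form records them; what is missing is a stated route in.

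Two things survive. Fellows are treated inconsistently, in content that belongs in a protocol. And participation is voluntary, with no described step that reaches people who do not enter the crossover. An analysis plan can report who responded, but it cannot change who was asked.

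**Conclusion.** The point holds as a risk to the first aim, together with a plain inconsistency about fellows. The inconsistency is certain: fellows are eligible, they are absent from the invitation, and they make up 0 of 26. The selection risk is conditional: prevalence is biased only if staff who decline or cannot do the crossover differ in symptoms from those who join, and the direction is open.

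Its size cannot be fixed from the protocol. On the assumptions above it runs from nothing (no fellows, full uptake) to bounds 46.7 points wide (4 fellows, 16 of 26 joining). That the group surveyed is self-selected or incomplete is a possibility, not something the protocol establishes. The within-surgeon comparison of control and intervention days does not depend on any of this.

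**What to change.** Separate the survey from the crossover.

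1. Send the existing preliminary questionnaire to every eligible attending, resident and fellow at both sites, with the option to complete the survey only. Invite them to the crossover as a separate choice.
2. Calculate prevalence and impact over all survey responders, and report the response rate against the roster by role and site. State whether 26 is that roster or a recruitment target.
3. Make Enrollment Criteria, Sample size and Recruitment Methods agree on fellows: either add them to the invitation and the N, or remove them from the criteria.

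The cost is a change to the e-mail and consent wording, with no new instrument or staff. The downside is that the survey N and the crossover N will differ, so both must be stated. The change has to be made before enrollment.

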## ● Statistics

- Descriptive statistics to calculate the prevalence and impact of musculoskeletal symptoms
- Descriptive statistics to characterize demographic information on participants
- Linear mixed models: Used to test for an association between pain and the targeted micro-break intervention
- Statistical significance is set at 0.05 (Bonferroni adjustment for measurement on 11 body parts.)

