#### Body part discomfort scores

- 1 Not uncomfortable
- 2 Barely uncomfortable
- 3 Quite uncomfortable
- 4 Very uncomfortable
- 5 Extremely uncomfortable

|                 | 1                     | 2                     | 3                     | 4                     | 5                     |
|-----------------|-----------------------|-----------------------|-----------------------|-----------------------|-----------------------|
| Neck            |  |
| Shoulder, right |  |
| Shoulder, left  |  |
| Hand, right     |  |
| Hand, left      |  |
| Lower back      |  |
| Upper back      |  |
| Knee, right     |  |
| Knee, left      |  |
| Foot, right     |  |
| Foot, left      |  |

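### Does it matter that Methods gives the body part discomfort scale as 0-5 when the forms print 1-5?

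*Protocol*

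**What the plan says.** In the protocol's Methods, under assessment tools, the pre-surgery entry describes body part discomfort as a "validated survey with 0-5 score on the neck, shoulder R/L, hand R/L, lower/upper back, knee R/L, foot R/L". The same list refers the reader to the questionnaires reproduced later in the protocol.

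The score is printed on three of those questionnaires: pre-surgery, post-surgery control and post-surgery intervention. Each gives five labelled points, from "1 Not uncomfortable" to "5 Extremely uncomfortable", above a grid with columns 1 to 5.

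Under Study design, the outcome is defined as "Primary outcome= difference between self-reported body part discomfort score from before/after surgery". The Statistics section gives the analysis as "Linear mixed models: Used to test for an association between pain and the targeted micro-break intervention", and the error control as "Statistical significance is set at 0.05 (Bonferroni adjustment for measurement on 11 body parts".

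**The concern.** The two ranges describe the same measure, and it is the measure behind the primary outcome. Both are current text, and nothing elsewhere in the protocol reconciles them. Nor is a lost line in the PDF a likely cause: on all three forms the list of labels and the column headings both start at 1, and point 1 is already the no-discomfort category.

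Three things could be at stake.

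- **Levels.** A reader who relies on Methods would take a reported 1 as one step above the floor, when on the forms it means no discomfort.
- **Size of change.** A reader who expresses a change as a share of the range would divide by 5 instead of 4.
- **Validation.** Methods calls the survey validated and gives it a range that the forms do not have, so one could ask whether the version in use is the validated one.

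Had the pre-surgery and post-surgery forms used different codings, the primary outcome itself would have been biased. That possibility is the reason to check.

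**Working it through.** **Inputs.** Stated range 0 to 5 (Methods, assessment tools). Printed range 1 to 5 (all three forms). Significance level 0.05 over 11 body parts (Statistics). Sample size 26 (Sample size).

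**1. Body sites.** Methods lists neck 1 + shoulder 2 + hand 2 + back 2 + knee 2 + foot 2 = 11. Each form has 11 rows, and Statistics counts 11. The sites agree, so the mismatch is confined to the range.

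**2. Range.** For a scale from L to H scored in whole numbers, there are H - L + 1 levels, and the before/after change lies between -(H - L) and +(H - L).

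| | Stated 0-5 | Printed 1-5 |
|---|---|---|
| Levels | 5 - 0 + 1 = 6 | 5 - 1 + 1 = 5 |
| Floor | 0 | 1 |
| Ceiling | 5 | 5 |
| Possible change per site | -5 to +5 | -4 to +4 |

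The stated range is not reproduced by any form. The gap is 1 point at the floor and nothing at the ceiling. In between it is undefined, because Methods gives no labels for its 0-5 points.

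**3. The primary outcome.** The before and after forms share one coding. A participant with no discomfort at either time scores 1 - 1 = 0. If an analyst recoded the forms to start at 0, every score would fall by 1 and the change would be (after - 1) - (before - 1) = after - before. The change score does not depend on where the scale starts.

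**4. The model.** A linear mixed model does not use the theoretical range. Suppose someone stretched 1-5 onto 0-5, which the protocol does not ask for. Every change would be multiplied by (5 - 0)/(5 - 1) = 1.25. The treatment coefficient and its standard error would grow by the same factor, so the test and its p-value would stay the same.

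**5. Sample size and error rate.** The sample size is a head count, 9 + 8 + 9 = 26, with no standard deviation or effect in scale points behind it. The per-site level is 0.05/11 = 0.0045. Neither uses the range.

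**6. Decision rules.** The protocol sets no margin, responder definition, minimal important change or threshold on this score, so no rule gives a different answer under one range than under the other.

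**The case for a change.** The strongest case for acting is that this is the primary measure, the two statements flatly contradict each other, and correcting one of them would cost a single line. This is not a detail that could be left to a statistical analysis plan, because the protocol states a range its own forms do not have. A 1-point change is 1/5 = 20% of the stated range but 1/4 = 25% of the printed one, so a report that copied the range from Methods would misdescribe both the floor and the relative size of the effect.

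The contradiction stands, and so does the advice to report the scale as administered. The consequence for the plan does not. The misreading requires someone to ignore the verbal labels on the forms, and it concerns levels and percentages of range, neither of which the protocol defines as an outcome.

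The validation point goes further than the protocol can support. The source instrument is not named, and nothing in the text shows which range it uses or that the printed version departs from it. Naming the version would be good reporting practice, but its absence is not an error the protocol demonstrates.

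**Conclusion.** The discrepancy is genuine, but it is a clerical slip in a parenthetical description and no change to the plan follows. Its whole size is 1 point at the floor, five levels instead of six, and a possible change per site of -4 to +4 instead of -5 to +5. The before/after change, the comparison of control and intervention days, the sample size of 26 and the level of 0.0045 per site are the same whichever range is quoted. Anyone analysing the data will see scores from 1 to 5 with their labels and describe the scale that way.

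This rests on two assumptions: that the printed forms are the ones administered, and that the pre-surgery and both post-surgery forms keep the same coding. The protocol supports both. The conclusion would differ if a threshold or margin were later set in scale points or as a share of the range, since the range would then enter a decision.

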#### Demographic information

Today's date

---

What is your gender?

- Male
- Female
- Transgender
- Other
- Prefer not to answer

Other (please specify)

---

What is your age?

---

What is your height in inches?

---

What is your weight in pounds?

---

BMI

---

What is your dominant hand?

- Left
- Right
- Both

What is your surgical title?

- Resident
- Fellow
- Attending

What is your postgraduate year (PGY) equivalent level?

- PGY1
- PGY2
- PGY3
- PGY4
- PGY5

How many years of surgical training and/or practice have you completed?

- 0-1 year
- 2-5 years
- 6-10 years
- 11-20 years
- Over 20 years

How many days a week do you perform surgery?

---

How many cases do you perform on a surgery day?

---

Confidential

Page 2 of 4

What is the average duration of each case in hours?

Do you have an exercise routine?

Yes  
 No

How many days a week do you exercise?

What form of exercise(s) do you perform? (select all that applies)

Stretching  
 Yoga  
 Pilates  
 Strength training  
 Cardio training (running, walking, swimming, cycling, etc.)  
 Other

Other (please specify)

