#### GOAL and Surg-TLX subscales

[figure not shown]
Degree of difficulty- This procedure was:

[figure not shown]
Task Complexity: How complex was the procedure?

[figure not shown]
Distraction: How distracting was the operating environment?

Mental Demand: How mentally demanding was the procedure?

Physical demand: How physically demanding was the procedure?

Confidential

Page 2 of 3

**Body part discomfort scores:****1 Not uncomfortable****2 Barely uncomfortable****3 Quite uncomfortable****4 Very uncomfortable****5 Extremely uncomfortable**

|                 | 1                     | 2                     | 3                     | 4                     | 5                     |
|-----------------|-----------------------|-----------------------|-----------------------|-----------------------|-----------------------|
| Neck            |  |
| Shoulder, right |  |
| Shoulder, left  |  |
| Hand, right     |  |
| Hand, left      |  |
| Lower back      |  |
| Upper back      |  |
| Knee, right     |  |
| Knee, left      |  |
| Foot, right     |  |
| Foot, left      |  |

What was your primary position during the surgery?

Standing  
 Seated  
 Standing and Seated

What surgical equipments have you used during the case? (select all that applies)

Headlight  
 Robot  
 Laparoscopic equipment  
 Loupes  
 Microscope  
 Other

Other (please specify)

How often have you performed micro-break stretches?

Every 20 minutes  
 Every 30 minutes  
 Every 45 minutes  
 Every hour  
 Every 1.5 hours  
 Every 2 hours  
 Random time

How many micro-break stretches have you performed during the surgery?

Confidential

Page 3 of 3

| What is the impact of microbreak stretches have on... | Diminished            | Did not change        | Improved              |
|---|-----------------------|-----------------------|-----------------------|
| Physical performance                                  |  |  |  |
| Discomfort and pain                                   |  |  |  |
| Fatigue   |  |  |  |

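### A non-significant Surg-TLX/GOAL difference cannot show that control and OSMB cases are comparable; report differences with confidence intervals instead

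*Protocol*

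**What the plan says.** The Study design bullets (Protocol, Methods) describe a crossover within surgeons, restricted to open neck cases, with three surgical days per condition ("Control: 3 Non-OSMB surgical days", and the same number with OSMB). On differences between operations, the text makes two commitments in one sentence. The first is "We will adjust for surgical duration". The second is to "use Surg-TLX, and GOAL questionnaires to show no statistically significant difference between control and intervention surgical cases".

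The primary-outcome bullet returns to the subject with "Control the surgical environment and difficulty using Surg-TLX and GOAL questionnaires", followed at once by "The score should be statistically insignificant among various surgeries".

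Both post-surgery forms carry five rating items under the GOAL and Surg-TLX subscales: degree of difficulty, task complexity, distraction, mental demand and physical demand. The Statistics section names linear mixed models for pain and sets significance at 0.05, with a Bonferroni adjustment tied to the 11 body parts. It gives no margin, interval criterion or separate significance level for the Surg-TLX/GOAL comparison.

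**The concern.** Each surgeon's control and OSMB operations are different operations, so comparable difficulty is a reasonable thing to examine. The stated rule examines it the wrong way round. A non-significant test means that the data did not exclude zero difference. It does not mean that they excluded a difference large enough to matter. The rule also rewards weak data: fewer surgeons, fewer cases or noisier ratings all make it easier to satisfy.

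What is at stake is a sentence in the report saying that the cases were alike, offered as support for the primary result, when the same data could be compatible with a real imbalance.

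A lesser point concerns what is measured. The ratings are given after surgery and include items such as "Distraction: How distracting was the operating environment" and "Mental Demand: How mentally demanding was the procedure". OSMB could itself alter the answers, so a difference on those items need not reflect case mix.

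**Working it through.** **Plan's own figure.** The sample size is a headcount: 9 + 8 + 9 = 26. It reproduces, but it has no power basis, and nothing in the protocol links it to the comparability check.

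**Inputs from the protocol.** 26 surgeons; 3 control and 3 OSMB days each; significance level 0.05.

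**Assumptions, because the protocol does not give them.**
- The test is two-sided.
- The five items form one composite score.
- There is one case per day. The number is not fixed; the preliminary questionnaire asks "How many cases do you perform on a surgery day".
- The true imbalance d is in units of the within-surgeon case-to-case SD.
- The surgeon-by-condition SD, s, is 0 or 0.5.

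**Formula.** A paired t-test on surgeon means, with k cases per condition:
- SE = √((2/k + s²)/n)
- noncentrality = d/SE, with n − 1 degrees of freedom
- the chance of non-significance is the noncentral t probability between ±t(0.975, n − 1)

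**Numbers for n = 26, k = 3, d = 0.3.**
- s = 0: SE = √(0.6667/26) = 0.160; noncentrality = 0.3/0.160 = 1.87; critical t = 2.06; non-significant 56% of the time.
- s = 0.5: SE = √(0.9167/26) = 0.188; noncentrality = 1.60; non-significant 66% of the time.

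**Chance of a non-significant result over a range of true imbalances.**

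| Scenario | 0.2 SD | 0.3 SD | 0.4 SD | 0.5 SD |
|---|---|---|---|---|
| 26 surgeons, one case/day, s = 0 | 78% | 56% | 33% | 15% |
| 26 surgeons, one case/day, s = 0.5 | 82% | 66% | 46% | 27% |
| 26 surgeons, two independent cases/day, s = 0 | 60% | 28% | 8% | 1% |
| 26 surgeons, two cases/day correlated 0.5, s = 0 | 72% | 45% | 21% | 7% |
| 13 surgeons, one case/day, s = 0 | 87% | 77% | 63% | 47% |

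The 13-surgeon row is hypothetical. It shows only the direction: halving participation raises the chance of passing at 0.3 SD from 56% to 77%.

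**If every item must be non-significant.** With 26 surgeons, one case per day, s = 0, and all five items shifted by 0.3 SD and correlated 0.3 to 0.7 (assumed), simulation gives about 14% to 29%. If only one item shifted, the imbalance would be missed more often than that.

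**What a bare pass leaves open.** With s = 0 the 95% half-width is 2.06 × 0.160 = 0.33 SD. A result just short of significance therefore has an interval reaching about 2 × 0.33 = 0.66 SD.

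**Sample size does not rescue the rule.** For d = 0.05 (k = 3, s = 0), non-significance occurs 94% of the time with 26 surgeons, 51% with 1000 and 1% with 5000. The answer follows n, not any stated limit of comparability.

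**The case against.** The strongest reply is that little hangs on this check. The crossover is within surgeon, cases are restricted to open neck surgery, and duration is adjusted for. That stands. A reader might infer that the primary OSMB test is invalid, or that it proceeds only if the check is passed. The protocol says neither, and it gives no basis for sizing a bias in the discomfort score.

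Second, "Control the surgical environment and difficulty using Surg-TLX and GOAL questionnaires" can naturally be read as covariate control. A reader might infer that the scores are definitely left out of the model. That goes too far: the Statistics section lists no covariates at all, not even duration, and an analysis plan may exist. But the next sentence returns to non-significance, and duration is the only variable the text says it will adjust for. The wording needs clarifying on either reading.

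Third, "The score should be statistically insignificant among various surgeries" names neither condition and may only express an expectation across case types. It is weak corroboration. The point rests on the Study design sentence.

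Fourth, with a large sample a non-significant result can come with an interval narrow enough to support comparability. That is true, but the support then comes from the interval judged against a margin, and the protocol has no margin.

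Fifth, the percentages move both ways with assumptions that the protocol does not settle: single score or five items, cases per day, surgeon-by-condition variation. This is right. A reader should not take 56% as this trial's pass rate. With 26 surgeons on the one-case, s = 0 assumptions, a 0.5 SD imbalance would be detected 85% of the time.

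Finally, that OSMB changes the workload ratings is plausible but not documented, and surgeons cannot be blinded to their own stretching. Lack of blinding is therefore not counted as a fault here.

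**Conclusion.** The point holds, and should be fixed, as an error of inference in the protocol's current wording: non-significance alone cannot show that control and OSMB cases are comparable. This does not depend on any of the assumed figures.

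Its consequence is limited. The primary test is unchanged, and what is lost is the justification for a comparability statement placed behind it. At 0.3 within-surgeon SD, with 26 surgeons and one case per day, the illustrative chance of passing despite a true imbalance is 56% to 66% for one composite score. It is about 14% to 29% if all five items must pass and all shift together. The imbalance, SDs, correlations and cases per day are assumptions.

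**What to change.** - **Delete** the non-significance aim from the Study design sentence, keeping "We will adjust for surgical duration". Delete "The score should be statistically insignificant among various surgeries" from the primary-outcome bullet.
- **Report instead** the control-minus-OSMB difference in GOAL degree of difficulty and in Surg-TLX task complexity, each with a 95% confidence interval that allows for repeated cases per surgeon. Add case type by condition. Draw no comparability conclusion from a p-value.
- **Describe only**, by condition, distraction, mental demand and physical demand, since they are rated after surgery and OSMB may change them.
- **Keep the primary model as planned**, adjusted for duration. Reword "Control the surgical environment and difficulty using Surg-TLX and GOAL questionnaires" to mean one prespecified sensitivity model that adds GOAL difficulty, task complexity and case type, with sparse categories combined. Case type has six categories on the forms, so up to five extra parameters before combining. That is a reason to keep it out of the primary model.

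A formal equivalence test is not requested. With 26 surgeons, one case per day and no true difference, its power would be about 17% for an assumed margin of 0.3 SD and 84% for 0.5 SD (s = 0), or 4% and 66% with s = 0.5.

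The cost is protocol wording and one sensitivity model, with no new data collection. The downside is small: post-surgery ratings could absorb part of an OSMB effect, so the model that includes them is for sensitivity only.

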#### Task Complexity: How complex was the procedure?

[figure not shown]
Distraction: How distracting was the operating environment?

**Mental Demand:** How mentally demanding was the procedure?

Physical demand: How physically demanding was the procedure?

Confidential

Page 2 of 2

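### Physical performance, fatigue and mental focus are recorded only on OSMB days, as perceived effects of the stretches, so the crossover gives a control comparison for discomfort alone

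*Protocol*

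**What the plan says.** Under Purpose of the study, the Protocol's second aim is "To examine the influence of otolaryngology stretching micro-breaks (OSMB) on their physical performance, mental focus, and self-reported pain and discomfort". The outcome measures under Study design widen this slightly by adding fatigue: "Secondary outcome= impact of OSMB on physical performance, discomfort/pain, fatigue, and mental focus".

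The design is given as "Crossover study design", with two conditions: "Control: 3 Non-OSMB surgical days" and "Intervention: 3 OSMB surgical days".

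The Assessment tools list gives the control-day post-surgery form two components, the Surg-TLX/GOAL items and the body part discomfort score. The intervention-day form has the same two plus "Questions on OSMB". In the form itself, that extra block contains a grid headed "What is the impact of microbreak stretches have on", with rows for physical performance, discomfort and pain, fatigue, and mental focus, and the answers Diminished, Did not change and Improved.

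The Statistics section names linear mixed models for pain against the intervention, and a Bonferroni adjustment for the 11 body parts. It names no test for the secondary outcome.

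**The concern.** A crossover has control days so that each surgeon's state with stretching can be set against the same surgeon's state without it. The second purpose speaks of influence on performance and focus, which is a claim about effect. If those constructs are recorded only on stretch days, and only as the surgeon's view of what the stretches did, there is nothing to subtract. The surgeon is asked to do the comparing mentally, knowing the condition, just after having been asked to stretch.

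At stake is what can be concluded about two of the three things the second purpose sets out to examine. A share of surgeons answering Improved is a fair description of opinion, but it does not estimate a difference between OSMB days and control days. The gap is fixed by the data collection forms, so an analysis plan written later cannot close it.

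**Working it through.** The Protocol states no figure to reproduce here. The check compares the forms item by item and then counts.

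**Step 1. Where each construct is measured.**

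| Construct | In purpose 2 | In secondary outcome | Pre-surgery form | Post-surgery control form | Post-surgery intervention form |
|---|---|---|---|---|---|
| Discomfort/pain | yes | yes | 11 body part scores | 11 body part scores | 11 body part scores, plus grid row |
| Physical performance | yes | yes | none | none | grid row only |
| Mental focus | yes | yes | none | none | grid row only |
| Fatigue | no | yes | none | none | grid row only |

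The remaining content of the control form is case type, duration, difficulty, complexity, distraction, mental and physical demand, position and equipment. The Preliminary questionnaire covers demographics, ergonomics and symptom history. The Exit questionnaire asks two questions about future use and recommendation. Neither supplies a control-day value.

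**Step 2. Could a figure missing from the extracted text hide a control-day item?** The gaps on the control form sit beside the case-type, duration and GOAL/Surg-TLX items, and those beside the rating items are probably response scales. The Assessment tools list settles the point independently, since it gives the control day no outcome beyond the Surg-TLX/GOAL items and body part discomfort.

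**Step 3. Could the Surg-TLX items stand in?** They are on both forms. The mental item reads "How mentally demanding was the procedure", and the physical item is built the same way. Both rate the operation, not the surgeon's focus, performance or fatigue. Study design also uses Surg-TLX and GOAL to show that control and intervention cases do not differ. An item expected to show no difference, as evidence of comparable cases, cannot also be the outcome on which a difference is sought.

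**Step 4. Counts.** Inputs: N = 26 (Sample size section: 9 + 8 + 9 = 26) and 3 days per condition (Study design).

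- Control surgeon-days: 26 × 3 = 78. OSMB surgeon-days: 26 × 3 = 78. Total: 78 + 78 = 156.
- Days planned to carry a body part discomfort score: 156 of 156.
- Days planned to carry any item on performance, fatigue or focus: 0 of 78 control days and 78 of 78 OSMB days.
- Constructs with no control value: 3 of the 4 in the secondary outcome, and 2 of the 3 in purpose 2 (fatigue is not named there).

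**The case against.** The strongest reply is that outcome and instrument agree. The secondary outcome is worded as the impact of OSMB, and the grid asks about the impact of the stretches on the same four constructs. Such a rating can be given only on a day when stretches were done, as with the tertiary outcome of distraction and workflow. The mixed model is stated for pain, and no contrast between conditions is promised for the secondary outcome. This stands: a reader might infer that the outcome is mislabelled or that the Protocol contradicts itself, and the text does not support that. What remains is that the second purpose speaks of influence on performance and focus, and nothing marks the outcome as perception or as descriptive. The attribution wording can be used only on OSMB days, but the constructs themselves could be rated on any day.

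A reader might also infer that the crossover is wasted. It is not. It serves the primary outcome, which is measured before and after surgery on both kinds of day and also covers the pain part of purpose 2. No stated test, significance level or sample size depends on the grid. Nor do the documents say that a percentage answering Improved will be reported as an effect. That is a risk of interpretation, not a plan.

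Finally, neutral ratings would come from the same unblinded surgeons. This stands too: a control value supplies a comparator, but it does not separate expectancy from effect. The primary outcome, also unblinded self-report, shares that limit.

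**Conclusion.** The point holds as a gap in the design that is cheap to close. For discomfort, the crossover gives a comparison of OSMB with control days. For physical performance, fatigue and mental focus it gives none, so the trial can describe what surgeons thought the stretches did but cannot estimate an effect.

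The size is 3 of 4 secondary constructs and 2 of 3 constructs in purpose 2, or 0 of 78 planned control surgeon-days. The 78 assumes that all 26 surgeons take part and complete all 3 control days. Forms are completed per surgery, so the number of forms may differ from the number of days. The proportion with a control value is zero whatever the attendance. These are counts of missing measurements, and they do not estimate the size of any bias.

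The primary outcome and its analysis are unaffected. The change is worth making because two of the affected constructs are named in the study's purpose and the missing data cannot be supplied afterwards.

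**What to change.** **Preferred change.** Add three identically worded, condition-neutral ratings to both post-surgery forms: physical performance, fatigue and mental focus during this case, for example on a 1–10 scale. If a change score like that of the primary outcome is wanted, add fatigue and mental focus to the pre-surgery form as well. Define the secondary outcome for these constructs as the within-surgeon OSMB-minus-control difference, estimated with the same linear mixed model as the primary outcome. Keep the existing grid as a descriptive measure of perceived benefit.

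**If the items cannot be added.** Restate the secondary outcome, and the performance and focus parts of purpose 2, as perceived impact reported descriptively. This needs only a change of text, but gives up any claim of effect on those constructs.

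**Cost.** The preferred change adds three short items per case to existing forms, with no extra visits, staff or participants. The items would be unvalidated. They also bring three further secondary tests that the Bonferroni adjustment for 11 body parts does not cover, so the Protocol should label them exploratory or adjust for them. The change supplies a comparator and removes the attribution wording. It does not remove expectancy bias, and the Protocol should say so.
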